## 5.2 Number of Subjects

Approximately 20 subjects will be enrolled in this study.

Subjects in this clinical investigation shall be referred to as “subjects.” For the sample size justification, see [Section 10.1](#).

---

### 5.2.1 Replacement of Subjects

Subjects that are not DLT-evaluable may be replaced. A subject is non-DLT-evaluable if subject discontinues treatment for any reason other than a DLT prior to completing the DLT evaluation period (see [Section 7.4.1](#) for DLT details).

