#### **7.4 Dose Modification**

##### **7.4.1 Dose-cohort Study Escalation/De-escalation and Stopping Rules**

The DLT evaluation period (ie, DLT-evaluable period) will be the 4 weeks on AMG 420 treatment within the first treatment cycle, starting on day 1 (start of infusion). The DLT evaluation period may also be extended to assess events starting within the window in case the DLT definition is time dependent.

Treatment in AMG 420 cycle 1 will be considered complete and the subject will be DLT evaluable if the subject has completed the DLT evaluation period or experienced a DLT any time during the DLT evaluation period. A subject will be non-DLT evaluable if he/she drops out before completion of the DLT-evaluable period for reasons other than a

DLT. All available safety data for subjects who are non-DLT-evaluable will still be evaluated and considered in DLRT decisions (see also [Section 10.4.1.1.1.1](#)).

See [Section 5.2.1](#) for description of replacement of subjects.

A DLT will be defined as any of the events described below occurring in a subject during the DLT evaluation period unless clearly attributable to causes other than treatment with AMG 420. The CTCAE version 5.0 (see [Section 12.4](#)) will be used to assess toxicities/adverse events with the exception of CRS and TLS (see [Section 7.4.2.1.2.5](#) and [Section 12.12](#) for grading criteria of CRS and TLS, respectively).

- Death not clearly due to the underlying disease or extraneous causes.

Non-hematologic DLTs:

- Non-hematological adverse event grade 3 or higher, EXCEPT:
  - infection responding to antibiotic/anti-infective treatment within 48 hours
  - grade 3 fatigue or asthenia
  - grade 3 headache resolving to  $\leq$  grade 2 within 72 hours
  - grade 3 insomnia resolving to  $\leq$  grade 2 within 7 days
  - grade 3 fever resolving to  $\leq$  grade 2 within 72 hours
  - grade 3 nausea, vomiting, or diarrhea responding if successfully managed with optimal medical support and resolved within 72 hours
  - laboratory parameters of grade  $\geq$  3, not considered clinically relevant, and improved to grade  $\leq$  2 within 72 hours

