b High dose vasopressors (all doses are required for  $\geq 3$  hours): norepinephrine monotherapy  $\geq 20 \mu\text{g}/\text{min}$ , dopamine monotherapy  $\geq 10 \mu\text{g}/\text{kg}/\text{min}$ , phenylephrine monotherapy  $\geq 200 \mu\text{g}/\text{min}$ , epinephrine monotherapy  $\geq 10 \mu\text{g}/\text{min}$ ; if on vasopressin, vasopressin + norepinephrine equivalent of  $\geq 10 \mu\text{g}/\text{min}$ ; if on combination vasopressors (not vasopressin), norepinephrine equivalent of  $\geq 20 \mu\text{g}/\text{min}$ .

c All sites will ensure that CRS rescue medications are available on-site, including corticosteroids and (for sites in regions where tocilizumab is approved and available, eg, the US and Germany) 2 doses of tocilizumab per study subject.

#### 7.4.2.1.3 Permanent Discontinuation of AMG 420

AMG 420 treatment will be permanently discontinued in the event of:

- infusion-related reaction grade 4 (the infusion has to be stopped immediately)
- grade 4 CRS
- grade 2 or 3 CRS meeting any of the criteria listed below:
  - grade 2 or 3 CRS that does not improve to  $\leq$  grade 1 within 7 days
  - grade 3 CRS that does not improve to  $\leq$  grade 2 within 5 days
  - if a subject experiences 2 separate grade 3 CRS events
  - if a subject experiences repeat grade 2 CRS event after dose reduction
  - grade 3 CRS at the initial run-in dose of the first treatment cycle if a dose step is being used
- grade 3 or higher TLS
- neurologic events considered related to AMG 420 by the investigator and meeting one or more of the following criteria:
  - grade 3 neurologic event leading to treatment interruption and has not resolved to  $\leq$  grade 1 within 14 days despite infusion interruption
  - grade 3 neurologic event that recurs after dose reduction
  - grade 4 neurologic event
- DLT or other unmanageable toxicity unless a subject has a clear clinical benefit from treatment, the toxicity has resolved to  $\leq$  grade 1 or baseline and after consultation with the sponsor
- in case of re-appearance of the same grade 4 adverse event
- treatment interruption of more than 2 weeks or several interruptions exceeding a total of 14 days of treatment per cycle due to serious adverse events/adverse events
- possible DILI requiring permanent withholding as per [Section 7.4.3](#)
- non-manageable GvHD
- subjects who require more than 1 dose reduction
- disease progression as defined by revised IMWG response criteria

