	
protocol-required therapies, and significant treatment-emergent adverse events will also be provided.
 
Dose Limiting Toxicities
 
The analysis of the probability of DLTs will include data from DLT-evaluable subjects (see Section 7.4.1 for definition of DLT-evaluable). The primary analysis will only include DLTs that occur within the first cycle. If DLTs occur outside the first cycle, a sensitivity analysis will be performed where DLTs occurring outside of the specified time interval are included. The number and percentage of subjects reporting DLTs will be evaluated overall and by AMG 420 dose level and part.
 
Clinical Laboratory Tests
 
Clinical chemistry, hematology, and urinalysis data will be listed and reviewed for each subject. Values outside the normal laboratory reference ranges will be flagged as high or low on the listings. Depending on the size and scope of changes in laboratory data, the analyses of safety laboratory endpoints will include summary statistics over time and/or changes from baseline over time. Maximum shifts in grades of selected safety laboratory values between baseline and the worst on-study value may be tabulated.
 
Vital Signs
 
Vital signs data will be listed and reviewed for each subject. Depending on the size and scope of changes, the analyses of vital signs may include summary statistics over time and/or changes from baseline over time.
 
Electrocardiograms
 
Summaries over time and/or changes from baseline over time will be provided for all ECG parameters. Subjects' maximum change from baseline in QTcF will be categorized and the number and percentage of subjects in each group will be summarized. Subjects' maximum post baseline values will also be categorized and the number and percentage of subjects in each group will be summarized. All on-study ECG data will be listed, and select parameters of interest may be plotted.

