6.2 Dose Limiting Toxicity Evaluable Analysis Set

The analysis of DLT will be restricted to DLT-evaluable subjects. **DLT evaluable analysis set includes subjects who complete the DLT evaluable period or experienced a DLT anytime during the DLT evaluable period.** A subject will be not DLT evaluable if he/she drops out before completion of the DLT-evaluable period for reasons other than a DLT prior to completing the 4 weeks of AMG420 treatment.

The DLT window may also be extended to assess events starting within the window in case the DLT definition is time dependent.

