9.6.2 Adverse Events

The Medical Dictionary for Regulatory Activities (MedDRA) version 23.0 or later will be used to code all adverse events to a system organ class and a preferred term. The severity of each adverse event will be graded using CTCAE version 5.0 criteria with exception of CRS which will be graded according to adopted grading system in Lee et al, 2014 and TLS graded according to Cairo-Bishop criteria (refer to protocol Appendix 12). Where appropriate the tables will also be presented by worst grade.

Treatment-emergent adverse events will be summarized based on the number (%) of subjects experiencing events by MedDRA SOC and PT. The denominator for the percentage will be based on the number of subjects in the safety analysis set.

The subject incidence of adverse events will be summarized for

- **TEAE**
 - All treatment-emergent AEs
 - Grade 3 or higher treatment-emergent AEs
 - Treatment-emergent SAEs
 - Treatment-emergent AEs leading to interruption of investigational product
 - Treatment-emergent AEs leading to withdrawal of investigational product
 - Fatal treatment-emergent AEs
- **Treatment-related AEs**
 - All treatment-related AEs
 - Grade 3 or higher treatment-related AEs
 - Treatment-related SAEs
 - Treatment-related AEs leading to interruption of investigational product
 - Treatment-related AEs leading to withdrawal of investigational product
 - Fatal treatment-related AEs

The summaries that are displayed by SOC, PT and grade will be ordered by descending order of incidence of SOC, PT and grade with in each SOC for the total group.

Then summary of TEAEs, summary of TEAEs, TESAEs, Treatment-related TEAEs, and Treatment-related SAEs by SOC, PT and Grade will be generated for extramedullary subjects.

The above adverse event tables will not be created if two or fewer subjects experience the adverse event.

Dose Limiting Toxicities

The analysis of the probability of DLTs will include data from DLT-evaluable subjects (see Protocol Section 7.4.1 for definition of DLT-evaluable). The primary analysis will only include DLTs that occur during the DLT evaluation period. If DLTs occur outside the DLT evaluation period, a sensitivity analysis will be performed where DLTs occurring outside of the specified time interval are included. The number and percentage of subjects reporting DLTs will be evaluated overall and by AMG 420 dose level.

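### The evaluable-only DLT rate can understate dose-limiting intolerability, because cycle 1 stops for AMG 420-related toxicity that is not a listed DLT drop out of it

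*Protocol*

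**What the plan says.** **Who counts.** Protocol Section 5.2.1: "A subject is non-DLT-evaluable if subject discontinues treatment for any reason other than a DLT prior to completing the DLT evaluation period". It adds: "Subjects that are not DLT-evaluable may be replaced". SAP Section 6.2 has the same exclusion: "A subject will be not DLT evaluable if he/she drops out before completion of the DLT-evaluable period for reasons other than a DLT". Neither text separates a stop caused by the drug from one caused by, say, progression or withdrawal of consent.

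**What is analysed.** Protocol Section 10.4.2.3.1: "The analysis of the probability of DLTs will include data from DLT-evaluable subjects". SAP Section 9.6.2 says the same. If DLTs occur outside the window, "a sensitivity analysis will be performed where DLTs occurring outside of the specified time interval are included".

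**What a DLT is.** In Protocol Section 7.4.1 the main non-hematologic criterion is "Non-hematological adverse event grade 3 or higher, EXCEPT" a list of exceptions. The list includes "grade 3 fatigue or asthenia" with no time limit, and infection that responds to treatment within 48 hours. No criterion covers toxicity that ends treatment as such.

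**What ends treatment.** Protocol Section 7.4.2.1.3 requires permanent discontinuation for a longer list. It includes grade 2 CRS not down to grade 1 or lower in 7 days; "if a subject experiences repeat grade 2 CRS event after dose reduction"; adverse event interruptions of more than two weeks, or totalling more than 14 days in a cycle; and the need for more than one dose reduction. It also names other unmanageable toxicity alongside DLT, so the protocol itself treats the two as different.

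**The concern.** DLTs are the first item in the primary endpoint row. A subject who could not finish four weeks because of the drug carries information about tolerability, but the evaluable-set rule handles that subject like one who left for an unrelated reason. With about 10 subjects per dose level, one or two such stops are 10% to 20% of a cohort. A reader given only the evaluable-only rate and its interval could not tell a dose that everyone completed from one that several subjects had to stop for toxicity short of the DLT list.

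**Working it through.** **1. The plan's own figures reproduce.** Protocol Section 10.1 gives a 65% to 89% chance of seeing an event in 10 subjects: 1 − 0.9^10 = 65.1% and 1 − 0.8^10 = 89.3%. For Table 5-1, take the Beta(1,1) posterior mass in each interval (0–20%, 20–33%, above 33%) and divide by the interval's width. Over-dosing has the largest value at 2/4 (0.29, 1.13, 1.19), 3/6 (0.17, 1.04, 1.24) and 4/8 (0.10, 0.93, 1.28), as tabulated.

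**2. Can such a stop occur in cycle 1?** Yes, though some routes are more likely than others.

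- Grade 2 CRS unresolved at 7 days is possible. In the first-in-human study 10 of 12 CRS events were in cycle 1. All those below 800 µg/day were grade 1 by CTCAE, but 600 µg/day was not tested (Protocol Sections 3.2.2.4 and 5.4).
- Infection: one that responds within 48 hours is not a DLT. Section 7.8.2.6 bars dosing with active systemic infection needing intravenous therapy until the course is complete. If the course exceeds 14 days (an assumption), Section 7.4.2.1.3 ends treatment. Infections occurred in 65.7% of first-in-human subjects and device-related infections in 20.0%.
- Repeat grade 2 CRS after dose reduction is remote in 28 days. Table 7-3 has reduction considered only after two consecutive grade 2 cases, each with at least 72 hours off drug.

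**3. Direction.** Among treated subjects let p be the probability of a listed DLT and q the probability of a drug-related permanent stop without one. For simplicity, ignore unrelated dropouts.

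- Evaluable-only rate, with or without replacement: p/(1 − q)
- Listed DLTs over all treated: p
- DLT or drug-related stop over all treated: p + q

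Since p/(1 − q) > p, exclusion raises the listed-DLT proportion. Against the broader rate it falls short by p + q − p/(1 − q) = q(1 − p − q)/(1 − q), which is positive whenever q > 0 and p + q < 1.

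Suppose stopped subjects, if kept on drug, would have had a DLT with probability r. The full-window DLT rate is then p + qr. The evaluable-only rate is below it only if r > p/(1 − q), for example r > 22.2% at p = 20%, q = 10%.

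**4. Size at p = 20%.** The documents give no q; the range is assumed.

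| q | Evaluable-only p/(1 − q) | Listed DLTs, all treated | DLT or drug-related stop | Shortfall against last rate (points) |
|---|---|---|---|---|
| 5% | 21.1% | 20% | 25% | 3.9 |
| 10% | 22.2% | 20% | 30% | 7.8 |
| 20% | 25.0% | 20% | 40% | 15.0 |

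At p = 10% the shortfalls are 4.5, 8.9 and 17.5 points.

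**5. In counts.** Suppose 12 are treated, with 1 DLT and 2 drug-related stops that are replaced. The plan reports 1/10 = 10.0% (exact 95% CI 0.3% to 44.5%). Listed DLTs over all treated are 1/12 = 8.3%. DLT or drug-related stop is 3/12 = 25.0% (5.5% to 57.2%).

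**6. Do other outputs recover these subjects?** In part. The DLT sensitivity analysis changes the time window, not the subjects. SAP Section 9.6.2 plans tables of treatment-related events leading to withdrawal over all treated subjects, but says its adverse event tables are not produced when two or fewer subjects have the event. SAP Section 9.2 summarises reasons for ending treatment but does not count or list non-evaluable subjects.

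**The case against.** A reader might infer that the primary DLT rate is biased low and that the selection always favours the drug. The documents do not support that. Dropping a subject without a DLT removes a non-event, so 1/12 = 8.3% becomes 1/10 = 10.0%. Low bias in the listed-DLT rate needs stopped subjects to be at above-average DLT risk. That is plausible, but no figure supports it. The 25% in the example is a different endpoint, not a corrected value of the same one.

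Three further points stand.

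- The primary endpoint row also lists treatment-emergent and treatment-related adverse events, analysed in all treated subjects (SAP Section 9.6.1). The primary safety results as a whole therefore do not omit these subjects.
- Dose decisions do not rest on the evaluable-only rate. Protocol Section 7.4.1 has the DLRT consider safety data from non-evaluable subjects, and Table 5-1 is tabulated by treated subjects.
- The example changes no enrollment decision. Under the width-adjusted rule 1/10 falls in the under-dosing interval and 3/12 in the target interval, and Protocol Section 10.3 continues enrollment for both.

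What the objection leaves is reporting. The DLRT safeguard protects decisions rather than the published estimate. One or two such stops at a dose could leave the DLT rate and also lose their withdrawal table.

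**Conclusion.** The concern holds as a limit on what the reported rate conveys. The evaluable-only DLT rate can understate dose-limiting intolerability, by 3.9 to 15.0 points at p = 20% and q between 5% and 20%. This rests on two assumptions: the values of q, and the view that a drug-related permanent stop in the DLT period is relevant to tolerability. It does not show that the listed-DLT proportion is too low, nor that a dose decision would differ. Given the DLRT review and the all-treated adverse event analyses, this is a cheap improvement to the SAP and not a must-fix flaw.

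**What to change.** Leave the DLT definition, the evaluable set and the replacement rule as they are. Add to SAP Section 9.6.2, for each dose level and over all treated subjects, with exact (Clopper-Pearson) 95% confidence intervals:

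- (a) subjects with a protocol DLT;
- (b) subjects with a DLT or a permanent discontinuation for an AMG 420-related adverse event during the DLT period, using the investigator's relatedness assessment already collected.

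Exempt both rows from the two-or-fewer suppression rule. Add a listing of every non-evaluable or replaced subject with the reason. Present (a) and (b) together: (a) counts stopped subjects as DLT-free although they were not observed for the full window, and (b) counts drug-related stops as events. Apart from unrelated dropouts, the two bracket the full-window rate p + qr.

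The cost is SAP wording, two table rows and one listing, with a note in SAP Section 10 that these are additions. The downside is a supportive toxicity rate that may look less favourable. Whether the DLT definition itself should change is a clinical question for the sponsor and the DLRT, outside this point.

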### 5.2.2 Number of Sites

Approximately 15 investigative sites in the European Economic Area, Australia, Japan, and the US will be included in the study. Sites that do not enroll subjects within 4 months of site initiation may be closed. Additional countries or sites may be added if deemed necessary.

## 5.3 End of Study

### 5.3.1 End of Study Definition

**Primary Completion:** The primary completion date is defined as the date when the last subject is assessed or receives an intervention for the final collection of data for the primary endpoint(s), whether the study concluded as planned in the protocol or was terminated early.

The primary completion date is the date when data for the primary endpoint of phase 1b are last collected at month 6 after the last subject is enrolled.

If the study concludes prior to the primary completion date originally planned in the protocol (ie, early termination of the study), then the primary completion will be the date when the last subject is assessed or receives an intervention for evaluation in the study (ie, last subject last visit).

**End of Study:** The end of study (EOS) date is defined as the date when the last subject across all sites is assessed or receives an intervention for evaluation in the study (ie, last subject last visit), following any additional parts in the study (eg, LTFU), as applicable.

### 5.3.2 Study Duration for Subjects

It is anticipated that an individual subject will participate in the study for up to approximately 5 years.

This includes a screening period lasting up to 21 days, a treatment period lasting for a median of approximately 8 months, and a follow-up period lasting up to 5 years from the first dose of AMG 420.

The actual duration for individual subjects will vary depending upon tolerability of AMG 420, evidence of clinical progression, and willingness to participate in the study.

---

#### 5.4 Justification for Investigational Product Dose (AMG 420)

The primary purposes in phase 1b are to 1) confirm the safety and tolerability of the 400 µg/day dose level in subjects with or without extramedullary (EM) disease and 2) establish the safety and tolerability of the 600 µg/day dose level.

The rationale for dosing in this study is based on the observations and experiences with AMG 420 in the separate FIH study conducted by BI (1351.1), which suggests that a cIV administration is safe and has the potential to induce durable remissions in patients with RRMM. This BI 1351.1 study has identified the 400 µg/day dose level as a preliminary safe and effective dose, as this dose was well tolerated in n = 3 subjects, whereas 2 of 3 subjects treated at the 800 µg/day dose experienced DLTs. The 600 µg/day dose level was not evaluated in the FIH study. Subjects may benefit from higher exposures than are achieved at the 400 µg/day dose level; thus, safety and tolerability of the 600 µg/day dose level may be evaluated in this phase 1b study. The DLRT will convene and review all available safety, laboratory, and PK data from all subjects treated in phase 1b cohort 1 at the 400 µg/day dose before recommending evaluation of the 600 µg/day dose (phase 1b cohort 2). If the DLRT recommends the 600 µg/day dose to be safe and well-tolerated after reviewing the phase 1b cohort 2 data, the sponsor may propose changing the recommended phase 2 dose to 600 µg/day on the basis of interim data analyses.

#### 5.5 Patient Input on Study Design

Subject input was not obtained for this study.

### 6. Study Population

Investigators will be expected to maintain a screening log of all potential study candidates that includes limited information about the potential candidate (eg, date of screening).

Eligibility criteria will be evaluated during screening.

Before any study-specific activities/procedures, the appropriate written informed consent must be obtained (see [Section 12.3](#)).

Prospective approval of protocol deviations to recruitment and enrollment criteria, also known as protocol waivers or exemptions will not be provided.

#### 6.1 Inclusion Criteria

Subjects are eligible to be included in the study only if all of the following criteria apply:

- 
- 101 Subject has provided informed consent prior to initiation of any study specific activities/procedures
- 102 Age  $\geq$  18 years at the time of the signing of informed consent
- 103 Multiple myeloma meeting the following criteria:
- Pathologically-documented diagnosis of multiple myeloma that is relapsed or is refractory (see [Section 12.9](#)) as defined by the following:
    - Relapsed after  $\geq$  3 lines of prior therapy that must include a PI, an IMiD, and a CD38-directed antibody in any order during the course of treatment OR refractory to PI, IMiD, and CD38-directed antibody.
  - Measurable disease, defined by 1 or more of the following at time of screening:
    - serum M-protein  $\geq$  0.5 g/dL measured by serum protein electrophoresis (SPEP)
    - urinary M-protein excretion  $\geq$  200 mg/24 hours
    - Involved sFLC measurement  $>$  10 mg/dL, provided that the sFLC ratio is abnormal as per IMWG response criteria
- 104 Eastern Cooperative Oncology Group (ECOG) performance status of  $\leq$  2
- 105 Life expectancy of at least 3 months as per investigator's judgment at time of screening
- 106 Hematological function without transfusion support (within 7 days from screening assessment) as follows:
- ANC  $\geq$   $1.0 \times 10^9$ /L (without growth factor support)
  - platelet count  $\geq$   $50 \times 10^9$ /L (without transfusions), but  $\geq$   $25 \times 10^9$ /L if the marrow is replaced by  $\geq$  50% myeloma (unless receiving anticoagulation therapy then platelet count must be  $>$   $50 \times 10^9$ /L)
  - hemoglobin  $\geq$  7.0 g/dL (transfusions permitted no later than 48 hours before screening)
- 107 Renal function as follows:
- calculated or measured creatinine clearance  $\geq$  30 mL/min using the Cockcroft-Gault equation or via 24-hour urine collection with plasma and urine creatinine concentrations, respectively
- 108 Hepatic function as follows:
- aspartate aminotransferase (AST) and alanine aminotransferase (ALT)  $<$  3 x upper limit of normal (ULN)
  - total bilirubin (TBIL)  $<$  1.5 x ULN (unless considered due to Gilbert's syndrome)

